1. LIST OF ABBREVIATIONS

Acronym	Title
AE	Adverse event
ALT	Alanine transaminase
AL-P	Alkaline phosphatase
AST	Aspartate transaminase
EDP	Exposure during pregnancy
FT4	Free thyroxine
GOT	Glutamic oxaloacetic transaminase
GPT	Glutamic pyruvic transaminase
γ-GTP	γ-glutamyl transpeptidase
IEC	Independent Ethics Committee
IRB	Institutional Review Board
LDH	Lactate dehydrogenase isozyme
mBMI	modified body mass index
N/A	Not applicable
NIS	Non interventional study
NIS	Neuropathy Impairment Score
QOL	Quality of life
QOL-DN	Quality of Life-Diabetic Neuropathy
SAE	Serious adverse event
T4	Thyroxine
THAOS	Transthyretin-Associated Amyloidosis Outcomes Survey
TTR	Transthyretin
TTR-FAP	Transthyretin familial amyloid polyneuropathy
SRSD	Single Reference Safety Document
TSH	Thyroid-stimulating hormone

2. **RESPONSIBLE PARTIES**

[figure not shown]
The Good Post Marketing Study Practice officer

Principal Investigator(s) of the Protocol

N/A

[figure not shown]
Amen dment numbe r	Date	Substantial or administrative amendment	Protocol section(s) changed	Summary of amendments	Reason
		Amendment of the investigated contents	Sections 7.2.4, 7.3.2.10, 7.3.2.13, 8.2	If the dose of Vyndaqel is changed for the treatment of ATTR-CM, the investigation will be discontinued.	Since the special investigation of ATTR-CM (all-cases survey) will be conducted in association with the added indication of ATTR-CM, the withdrawal criteria for the investigation were set in order to prioritize registration to the investigation on major diseases for treatment.
5.0	28 March 2019	Other amendment(s)	Section 7.6	Additional descriptions of Sections 7.6.1 and 7.6.2 and improvement of descriptions of Section 7.6.5.2 accordingly	Additional descriptions due to amendment of a company template and improvement of descriptions accordingly, which will not affect the contents of investigation. Because the contents of descriptions were reexamined and improved.
	amendment(s)	Sections 8 and 9	Update of contents of descriptions	Amendment due to the amendment of a company template, which will not affect the contents of investigation.	
			All	Change of wording without change of meaning such as correction of errors in writing and unification/change, etc. of terms	Because the contents of descriptions were reexamined and improved.
4.0	1 December 2018	Other amendment(s)	Study items	Correction of errors in writing	Because of errors in writing

3. AMENDMENTS AND UPDATES

VYNDAQEL B3461042 NON-INTERVENTIONAL STUDY PROTOCOL Amended, 28 Mar 2019

		Other amendment(s)	Definitions of safety events	The definition of "discontinuation of treatment" was changed to "drug withdrawal".	Due to reexamination of Japanese translation
		Other amendment(s)	NAME, ADDRESS AND OUTSOURCE D OPERATION S OF THE PERSON WHO WAS CONTRACTE D WITH THE OPERATION S	Addition of a contractor	Addition as a result of establishment of Pfizer R&D Japan G.K.
		Other amendment(s)	CONTACT INFORMATI ON	Change of the company name	Change as a result of establishment of Pfizer R&D Japan G.K.
	19 May 2017	Amendment of the planned contents	Study items	Addition of "confirmation of survival"	Because it was necessary to confirm the survival status
		Other amendment(s)	Registration items	Addition of "Presence or absence of having received/used Vyndaqel at other sites, and if Yes, patient's duration of treatment (name of the site if the treatment period is 3 years or longer)"	Because patients who have received/used Vyndaqel at other sites for more than 3 years are not subject to this study
3.0		Other amendment(s)	Study items	Change in the timing of evaluation of physical symptoms	Because there was inconsistency with the CRF
		Other amendment(s)	Observation period	The observation period for subjects who discontinued the treatment was clearly stated.	Because the observation period was accurately described
		Other amendment(s)	Planned period of investigation	It was described as "the transition to registration only after the registration period will be implemented after consultation with the PMDA".	Added as instructed by PMDA

VYNDAQEL B3461042 NON-INTERVENTIONAL STUDY PROTOCOL Amended, 28 Mar 2019

		Other amendment(s)	All	Correction of errors in writing	Because of errors in writing
2.0	10 August 2015	Other amendment(s)	All Adverse events	Response to a new company form	The form used in the company was changed and the description of requirements for reporting of adverse events which had been handled as Appendix was added to the text, and other items to be described were added. Therefore, a new form was applied.
		Other amendment(s)	Observation period	The definition of patients whose observation period is 1.5 years was changed from "Patients registered after May 2018" to "Patients who started to receive Vyndaqel after May 2018".	The definition of patients with the observation period of 1.5 years was accurately described.
1.1	7 November 2013	Other amendment(s)	Patient registration	Additional description of FAX number of Patient Registration Center	Because new information was obtained
1.0	8 October 2013	N/A	N/A	N/A	N/A

4. MILESTONES

Milestone	Planned date
Start of data collection	November 2013
End of data collection	May 2021
Final study report	To be determined

5. RATIONALE AND BACKGROUND

Transthyretin familial amyloid polyneuropathy (TTR-FAP) is a rare, highly heritable disease in which amyloid derived from transthyretin (TTR) is deposited in the peripheral and autonomic nervous systems, thereby causing dysfunction. In Japan, patients are accumulated in Nagano and Kumamoto prefectures. It is known that the onset of the disease in the accumulated area is young in the 30s and the duration of survival after the onset is approximately 10 years, which is extremely poor prognosis. However, the only treatment for TTR-FAP in Japan has been symptomatic treatment for each of the various symptoms associated with the disease. Liver transplant has been performed as the only method to suppress the

> Pfizer Confidential Page 10 of 37

disease progression, but the target patients for liver transplant are very limited due to problems such as lack of donors and risk of transplant surgery.

Vyndaqel (generic name: tafamidis meglumine) is a therapeutic agent for TTR-FAP with a novel mechanism of action that suppresses amyloid formation by binding to the thyroxine (T4) binding site of the TTR tetramer, stabilizing the TTR tetramer, and inhibiting its dissociation into monomers. The overseas clinical studies started in 2007 demonstrated the efficacy of Vyndaqel not only in delaying the progression of peripheral neuropathy, suppressing the decline of quality of life (QOL) and improving nutritional condition in patients with TTR-FAP but also in stabilizing TTR early after the start of treatment and maintaining TTR stabilization throughout the study period. As a result, Vyndaqel was approved in Europe in November 2011 and has been in the market. In Japan, the phase 1 study confirmed no difference in pharmacokinetics, TTR stabilization, and safety between Japanese and non-Japanese subjects. Furthermore, the domestic phase 3 clinical study in Japanese adult patients with TTR-FAP also demonstrated the efficacy and safety of Vyndaqel equivalent to those in the results of the overseas clinical studies. As a result, the application for approval was filed in February 2013 and the drug was approved in September 2013.

The Special Investigation of Vyndaqel Capsules - Investigation on long-term use - (hereinafter referred to as this study) will be conducted to comprehend information on the safety (e.g., onset status of adverse reactions) and efficacy of Vyndaqel in the long-term use under the post-marketing actual use in patients receiving Vyndaqel Capsules (hereinafter referred to as this drug). This study will be conducted in all patients receiving this drug on the basis of the conditions for approval. The information collected in this study will be used to provide information on proper use and prepare application dossiers for reexamination. Therefore, this study must be conducted in strict compliance with the "Ordinance Concerning Standards for Conducting Post-Marketing Study and Studies on Pharmaceutical Products" (MHLW Ordinance No. 171 dated December 20, 2004). The case data collected in this study will be reported to the Ministry of Health, Labour and Welfare (MHLW) according to the Pharmaceuticals and Medical Devices (PMD) Act. In this case, the data may also be publicly posted in MHLW's "Pharmaceutical and Medical Device Safety Information" and "Pharmaceuticals and Medical Devices Information Website" (http://www.info.pmda.go.jp) as a listing of patients, which will include the information on names of drugs, adverse reactions, gender, and age (increment of 10 years). Furthermore, data collected may also be disclosed if the MHLW is required to disclose such information in accordance with the "Act on Access to Information Held by Administrative Organs" (Law No. 42 dated May 14, 1999); provided that in no event will the names of physicians, medical institutions, and other personal information be subject to such disclosure, nor will it be posted or disclosed in any form or shape.

6. RESEARCH QUESTION AND OBJECTIVES

To understand information on the safety (e.g., onset status of adverse reactions) and efficacy of this drug in the long-term use under the post-marketing actual use in all patients receiving this drug. Review on the onset status of hepatotoxicity will be set as a major investigation item in this study.

[Conditions for approval]

Because the number of study participants in Japan is very limited, a drug use investigation in all patients should be conducted during the reexamination period to grasp the background information on patients using this drug, collect data on the safety and efficacy of this drug early, and take necessary measures for proper use of this drug.

6.1. Safety specifications

[Important potential risks] Hepatotoxicity, hypersensitivity reaction, reproductive and developmental toxicity, infection

[Important missing information] Patients with severe hepatic impairment

7. RESEARCH METHODS

7.1. Study design

This study is a multi-center, cohort study of patients receiving/using this drug. The investigators complete the case report form (CRF) based on the information extracted from the medical charts created in daily medical practice.

7.2. Setting

All patients who received/used this drug will be targeted in this study.

The indication, dosage and administration, and contraindications of this drug are as follows. When using this drug, refer to the latest package insert of this drug.

[Indication] Suppression of progression of peripheral neuropathy in transthyretin familial amyloid polyneuropathy (TTR-FAP)

[Dosage and administration] The usual adult dosage for oral use is 20 mg of tafamidis meglumine once daily.

[CONTRAINDICATIONS] Patients with a history of hypersensitivity to any of the ingredients of this drug

7.2.1. Sites for this study

This study will be conducted at all sites and medical departments that use this drug.

7.2.2. Duration of study

The planned period covered by this study is as follows.

Duration of study: November 2013 to May 2021 (7.5 years)

Registration period: November 2013 to November 2019 (6 years)

A contract will be concluded after the start date of the study period, and then, the patient registration will be started. The transition to registration only after the registration period will be implemented after consultation with the Pharmaceuticals and Medical Devices Agency (PMDA).

7.2.3. Study procedures

7.2.3.1. Study method

This study will be conducted by all-cases survey (including retrospective survey).

7.2.4. Observation period

3 years from the first day of treatment with this drug (156 weeks) However, the observation period for patients who started to receive this drug after May 2018 will be 1.5 years (78 weeks).

> Pfizer Confidential Page 12 of 37

If the treatment with this drug is discontinued during the observation period, the observation period will be until the day of discontinuation. If the dose of this drug is changed for the treatment of ATTR-CM, the observation period will be up to the date of last dose of 20 mg.

This study will be conducted using booklet type CRF.

The safety and efficacy assessments will be performed at the first visit (including the end date of the observation period) on or after the end date of the observation period (day of discontinuation if the treatment is discontinued during the observation period or date of the last dose of 20 mg if the dose was changed for the treatment of ATTR-CM). However, if a subject is lost to follow-up halfway through, the safety and efficacy assessments will be performed using the information on the last visit date.

Booklet No.	Observation period	
Booklet 1	First day of treatment to Week 78 (1.5 years)	
Booklet 2	Week 79 to Week 156 (3 years)	

7.3. Registration items and study items This study will be conducted according to the following schedule of observation.

Table 1. Schedule of observation

			Booklet 1		Book	det 2
Item	Registr ation form	At start of the study	Week 52 (1 year)	Week 78 (1.5 years)	Week 104 (2 years)	Week 156 (3 years)
Information to identify the subject			-	-	-	-
First day of treatment with this drug			-	-	-	-
Presence or absence of having received/used this drug at other sites, and if Yes, patient's duration of treatment	•					
THAOS registration status/THAOS registration ID						
State of concurrent medical examination	-					→
Background variables	-		-	-	-	-
History of previous treatment drugs for the targeted disease	-	•	-	-	-	-
Targeted drug use record	-	•				>
Concomitant therapy (drug therapy/ non-drug therapy)	-	•				
General tests (height, body weight, pulse, blood pressure)	-	•				
Clinical laboratory tests	-	•				→
Plasma concentration of tafamidis (to be performed only for patients with severe hepatic impairment)	-					•
Cardiovascular evaluation (ECG, echocardiography)	-					
Assessment of neurological function (NIS)	-		-		-	
Quality of Life (QOL-DN)	-		-		-	
Ambulatory state	-		-		-	
Neurological assessment (motor function, tendon reflex, tactile sense, pain sensation, vibration sense, positional sense)	-	•	•	-	•	•
Medical assessment of physical symptoms	-	←		-		
Pregnancy	-	•				→
Record of study discontinuation	-					► ►
Confirmation of description concerning adverse events corresponding to major investigation item	-					→
Adverse events and tests for adverse events	-	◀				── →
Confirmation of survival						

Pfizer Confidential Page 14 of 37

7.3.1. Registration items

Enter the following information at the start of treatment with this drug in the registration form. The day when the treatment with this drug is started will be defined as "first day of treatment". However, for subjects who participated in the clinical studies (including post-marketing clinical studies), the day when the treatment with a commercially available product of this drug is started will be defined as "first day of treatment". For patients who have received/used this drug at other sites, the day when the treatment is started at the own site will be defined as "first day of treatment"*. However, if the drug is prescribed at another site and only the diagnosis of TTR-FAP is made at the own site, the day when the treatment with this drug is started at another site will be defined as "first day of treatment".

*If the patient has been receiving this drug for more than 3 years at the first day of treatment with this drug at the own site and the name of the site is known, only the patient registration will be made.

(1) Name of site/department

(2) ID number

(3) Gender

(4) Date of birth (age at the start of treatment with this drug at the site if the information cannot be disclosed)

(5) First day of treatment with this drug

(6) Presence or absence of having received/used this drug at other sites, and if Yes, patient's duration of treatment (name of the site if the treatment period is 3 years or longer)

For sites participating in THAOS** at the time of registration, the following information should also be entered:

(1) THAOS registration status

(2) THAOS case number

**THAOS (Transthyretin-Associated Amyloidosis Outcomes Survey) is a multinational disease registry of all patients with TTR-associated amyloidosis (hereinafter referred to as ATTR) and participants who are not diagnosed with ATTR but have TTR mutations.

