Survival time will be evaluated by setting death as the event of interest. For patients who complete the study, survival status will be determined on the first follow-up date exceeding 3 years after the start of treatment with this drug at the own site. In the case of death, information on the cause, i.e., whether the death is due to TTR-FAP or to another cause (including unknown) will also be collected. *For patients who started the treatment with this drug after May 2018 (1.5-year observation period), their survival should be confirmed using the attached CRF* on the first follow-up date exceeding *1.5 years after the start of treatment at the own site.* 

The following two kinds of event will be evaluated:

- Death from any cause
- FAP-related death (Death from TTR-FAP is set as the event of interest. Death with missing cause will
  not be regarded as an event of interest.)

Time to event will be evaluated with respect to the following two kinds of time:

- Time from start of treatment to event
- Time from onset of FAP to event

CC				
I				
l				

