## Exposure of this drug

Using the SAS, exposure of this drug will be summarized with respect to the following aspects:

- Duration of treatment [<52 weeks, ≥52 to <78 weeks, ≥78 to <104 weeks, ≥104 to <156 weeks, ≥156 weeks]

- − Initial daily dose [<20 mg, 20mg, ≥20 mg]
- Total number of treatment weeks (continuous, non-dosing periods excluded, unit: weeks)
- Total dose administered (continuous)

The duration of treatment is defined as the length of the time from the date of first dose to the last dose in this study, including non-dosing periods. If the patient remains on the treatment at the end of observation period, the duration of treatment will have the value ">156 weeks".

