#### **Onset timing of adverse reactions**

Adverse reactions will be summarized by timing of first onset [<26 weeks,  $\geq$ 26 to <52 weeks,  $\geq$ 52 to <78 weeks,  $\geq$ 78 to <104 weeks,  $\geq$ 104 to <156 weeks,  $\geq$ 156 weeks] for each SOC and PT in terms of n and proportion. When calculating the proportion, the denominator will be the number of patients in each category of onset time who received at least one dose.

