#### 8.2.4.7. Subgroup analyses

For the measured values of NIS-LL score and TQOL and the changes from the baseline at each time point in A1.1, summary statistics will be calculated for each factor specified in Section 5.4. For prior treatments and concomitant medications, whether to perform subgroup analysis for which treatment/medication will be examined prior to analysis and recorded in order to perform more appropriate evaluation.

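### Former trial participants and unlinked patients from other sites keep a reset time zero, and onset timing, most efficacy tables and survival from start of treatment are not visibly split by past treatment

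*Protocol*

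**What the plan says.** **Time zero.** Protocol 7.3.1 has two resetting rules. For participants in earlier clinical studies, "the day when the treatment with a commercially available product of this drug is started will be defined as" the first day of treatment. For patients who had the drug at another site, "the day when the treatment is started at the own site will be defined as" the first day, unless the own site only made the diagnosis. A footnote limits this: "If the patient has been receiving this drug for more than 3 years at the first day of treatment" at the own site, "and the name of the site is known, only the patient registration will be made". That first day anchors the observation period, the booklets, the baseline values and the survival check.

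**Linkage.** SAP 8.2.1 identifies patients seen at several sites at a case conference. It combines their data and uses the earlier site's start date as origin.

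**Analyses on this clock.**
- SAP 8.2.3.1: "Adverse reactions will be summarized by timing of first onset", in classes from under 26 weeks upward, over the whole safety set.
- SAP 8.2.4.1 to 8.2.4.5: change from the value before treatment, with a baseline window that runs to Week 4 (Appendix 1).
- SAP 6.2 and 8.2.4.6: "Time from start of treatment to event", alongside time from disease onset.
- SAP 8.2.2: exposure, measured "from the date of first dose to the last dose in this study".

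**Past treatment as a factor.** SAP 5.4 lists past treatment with the drug (present, absent). SAP 8.2.3.3 applies the 5.4 factors to any adverse reaction, and to hepatotoxicity if it is frequent enough. SAP 8.2.4.7 applies them "For the measured values of NIS-LL score and TQOL and the changes from the baseline at each time point in A1.1".

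**The concern.** The objectives are the onset of adverse reactions, with hepatotoxicity as the major investigation item, and efficacy in long-term use. Both depend on time since the drug was started. A patient who rolls over from a trial, or arrives from another site and is not linked, is placed at Week 0 with treatment already behind them.

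Three things follow for such a patient. The baseline is not a pre-treatment value, so change from baseline compares one treated state with another. A reaction in the first onset class may belong to a much later stage of real exposure. Survival from start of treatment is conditional on having lived through the earlier treatment. When these patients share a table with new users, the reader cannot tell which kind of time is being shown.

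**Working it through.** **1. Scale of the study.** The only size figure in the plan reproduces: 0.87 × 127.54 = 110.96 and 1.1 × 127.54 = 140.29, against the stated 111 to 140 patients. This figure is not in dispute. It shows that a handful of patients is a visible share. If 10 to 20 were pre-treated (an assumption), that is 10/140 = 7% to 20/111 = 18%.

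**2. Which patients keep a reset origin.**

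| Patient | Origin in Protocol 7.3.1 | Repair in SAP 8.2.1 | Origin analysed |
|---|---|---|---|
| New user | first dose | not needed | true start |
| Other site, linked | own-site start | earlier site's date | earlier site's start |
| Other site, not linked | own-site start | none | reset |
| Trial roll-over | commercial start | none for trial exposure | reset |

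Linkage relies on birthdate, sex, genotype and site names. Registration may give age instead of birthdate, and registration item (6) asks for the earlier site's name only at 3 years or more of prior use. Some failures are therefore possible; their number is not given.

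**3. Where past treatment is separated.**
- Split: any adverse reaction, NIS-LL, TQOL.
- Split only if incidence suffices: hepatotoxicity.
- Not split in the visible text: onset timing, total NIS, NIS-UL, mBMI, ambulatory status, neurological scores, survival from start of treatment.

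**4. Onset class.** With prior exposure of T weeks, the class below 26 weeks covers real exposure from T to T + 26. For T = 52 (assumed), that is weeks 52 to 78.

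**5. Pooled early incidence.** Let f be the pre-treated share: pooled = (1 − f) × risk in new users + f × risk in pre-treated. Assume 20% in new users.

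| f | pre-treated 20% | pre-treated 10% | pre-treated 5% |
|---|---|---|---|
| 0.1 | 20% | 19% | 18.5% |
| 0.3 | 20% | 17% | 15.5% |
| 0.5 | 20% | 15% | 12.5% |

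**6. Three-year survival from the analysed origin.** Protocol section 5 puts survival after onset at about 10 years; this is used as a Weibull median: S(t) = exp(−ln 2 × (t/10)^k). Assume treatment starts d = 5 years after onset and prior exposure is T = 3 years.
- k = 1 (constant hazard): exp(−0.693 × 0.3) = 0.812 for new and pre-treated alike. No bias.
- k = 2 (rising hazard), new users: S(8)/S(5) = exp(−0.693 × (0.64 − 0.25)) = 0.763.
- k = 2, pre-treated: S(11)/S(8) = exp(−0.693 × (1.21 − 0.64)) = 0.674.
- Pooled at f = 0.1, 0.3, 0.5: 0.754, 0.736, 0.718.
- Deaths before the reset origin, never seen: 1 − S(8)/S(5) = 23.7% of those who truly started.

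A falling hazard would move the pooled figure the other way. f, d, T, k and the risks are all assumptions.

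**The case against.** The plan contains more repair than Protocol 7.3.1 alone suggests. Every site using the drug takes part, all patients are targeted, and completeness of registration is checked yearly with each site. An earlier commercial site should therefore hold a record, and linkage should undo the reset for most patients who changed site. This stands, and it narrows the problem mainly to trial roll-overs. The approval condition calls the number of Japanese study participants very limited.

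Four stronger readings are tempting, and the documents do not support them.
- *Hepatotoxicity is always pooled.* SAP 8.2.3.3 splits it by the 5.4 factors if incidence is sufficient.
- *Exposure is mislabelled.* SAP 8.2.2 openly defines it as exposure within the study. What is missing is cumulative exposure.
- *Pooling is known to dilute early reactions or distort survival in a given direction.* With equal risks or a constant hazard it does neither. Time from disease onset, the other survival scale, does not have its origin moved by the reset.
- *Long-term users routinely enter as new.* More than 3 years of prior use at a known site means registration only. With approval in September 2013, commercial use of that length arises only from late 2016. The route left open is an unknown site or trial use, whose length is not given.

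The outline of survival case handling in SAP 8.2.4.6 is a figure not shown, and some sections are redacted. A split there cannot be excluded.

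**Conclusion.** The point holds in limited form. Nothing visible re-anchors trial exposure, and unlinked other-site patients also keep the later origin. Onset timing, most efficacy tables and survival from start of treatment then mix two kinds of time zero without a visible split.

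The size is unknown. The illustrations run from no effect to a fall from 20% to 12.5% in early incidence, or from 0.763 to 0.718 in three-year survival, each at an assumed pre-treated share of one half. They show sensitivity and do not estimate the bias in this study.

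A reader might also infer that treatment-naive patients should replace all patients as the main population. That does not follow: the stated objective covers everyone receiving the drug, and the study is descriptive with no hypotheses. This is a cheap improvement in presentation and does not invalidate the plan.

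**What to change.** Keep the all-patient results and add the following.
- **SAP 8.2.3.1** (onset timing, and hepatotoxicity counts whatever their incidence), **8.2.4.1 to 8.2.4.5**, and **8.2.4.6** for time from start of treatment: show the same results by past treatment with the drug, absent or present, as determined after data linkage. Show unknown separately, since SAP 8.2.2 has that category and 5.4 does not.
- **SAP 5.4:** state that past treatment includes use in clinical studies. The CRF item on treatment experience does not spell this out.
- **Interpretation:** base statements about early onset and about change from a pre-treatment baseline on the treatment-naive column.
- **SAP 8.2.2:** keep in-study exposure as defined, and add prior duration where registration item (6) gives it. Give unknown prior duration its own class; it will include trial exposure, for which no duration item is listed.

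The cost is SAP wording and extra columns from fields already collected. The downside is small, imprecise strata, most of all in the pre-treated column.
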